11.2.1 Serious Adverse Experience Reporting

The PI will document all SAEs that occur (whether or not related to study drug) on an SAE Report Form. The collection period for all SAEs will begin after informed consent is obtained until all procedures for the final study visit have been completed.

All SAE Report Forms will be reviewed by the PI. SAE reports that are both related and unexpected will be sent to FDA within one business day of learning of the event. SAE reports that are both related and unexpected will also be forwarded to the UW Institutional Review Board, in accordance with UW Standard Operating Procedures. Because this is an observational study, no data safety and monitoring board will be created for this trial. Adverse events and recruitment will be monitored by the PI and reported to the UW IRB, as described above.

12 DISCONTINUATION AND REPLACEMENT OF SUBJECTS

12.1 Early Discontinuation of Study Drug

A subject may be discontinued from study treatment at any time if the subject, the investigator, or the Sponsor feels that it is not in the subject's best interest to continue. The following is a list of possible reasons for study treatment discontinuation:

- Subject withdrawal of consent
- Subject is not compliant with study procedures
- Adverse event that in the opinion of the investigator would be in the best interest of the subject to discontinue study treatment
- Protocol violation requiring discontinuation of study treatment
- Lost to follow-up
- Sponsor request for early termination of study
- Positive pregnancy test (females)

If a subject is withdrawn from treatment due to an adverse event, the subject will be followed and treated by the Investigator until the abnormal parameter or symptom has resolved or stabilized.

All subjects who discontinue study treatment should come in for an early discontinuation visit as soon as possible and then should be encouraged to complete all remaining scheduled visits and procedures.

All subjects are free to withdraw from participation at any time, for any reason, specified or unspecified, and without prejudice.

Reasonable attempts will be made by the investigator to provide a reason for subject withdrawals. The reason for the subject's withdrawal from the study will be specified in the subject's source documents Refer to Section 10 for early termination procedures.

12.3 Withdrawal of Subjects from the Study

A subject may be withdrawn from the study at any time if the subject, the investigator, or the Sponsor feels that it is not in the subject's best interest to continue.

All subjects are free to withdraw from participation at any time, for any reason, specified or unspecified, and without prejudice.

Reasonable attempts will be made by the investigator to provide a reason for subject withdrawals. The reason for the subject's withdrawal from the study will be specified in the subject's source documents. Subjects who withdraw after Visit 2 but prior to Visit 10 will be encouraged to come in for a final visit (and the procedures to be followed would include those for their next scheduled visit).

12.4 Replacement of Subjects

Subjects who withdraw from the study treatment will be replaced.

Subjects who withdraw from the study will be replaced.

13 PROTOCOL VIOLATIONS

A protocol violation occurs when the subject or Sponsor-Investigator fails to adhere to significant protocol requirements affecting the inclusion, exclusion, subject safety and primary endpoint criteria. Protocol violations for this study include, but are not limited to, the following:

- Failure to meet inclusion/exclusion criteria
- Use of a prohibited concomitant medication
- Failure to comply with Good Clinical Practice (GCP) guidelines will also result in a protocol violation. The Sponsor-Investigator will determine if a protocol violation will result in withdrawal of a subject.

When a protocol violation occurs, it will be discussed with the Sponsor-Investigator and a Protocol Violation Form detailing the violation will be generated. This form will be signed by a Sponsor-Investigator. A copy of the form will be maintained in the regulatory binder and in the Sponsor-Investigator's files.

14 STATISTICAL METHODS AND CONSIDERATIONS

14.1 Data Sets Analyzed

All participants who receive the study drug (D₆-25(OH) D₃ Solution for Injection) will be included in the safety analysis.

14.2 Demographic and Baseline Characteristics

The following demographic variables at screening will be summarized by CKD status and race: age, gender, medical comorbidities, medications used, height, weight, body mass index, laboratory values (including calcium, phosphorus, albumin, vitamin D binding protein, parathyroid hormone, fibroblast growth factor-23), and adiposity measured by DXA.

14.3 Analysis of Primary Endpoint

We will examine the distribution of D₆-25(OH) D₃ clearance by CKD status (3 categories) and race (2 categories) using box plots and summary statistics. We will explore the distribution of D₆-25(OH) D₃ clearance by key covariates (age, gender, diabetes status, and baseline concentrations of 25(OH)D, PTH, FGF-23, and vitamin D binding protein) using locally weighted scatterplot smoothing (LOWESS), cubic splines, and box plots. We will pay particular attention to the associations of PTH and FGF-23 with D₆-25(OH) D₃ clearance, including multivariable modeling to determine independent associations. We will test associations of CKD status and race with D₆-25(OH) D₃ clearance (continuous outcome variable) using linear regression. Models will be adjusted for age, gender, diabetes status, vitamin D supplement use (within eligibility criteria), body size, baseline 25(OH)D concentration, and other covariates strongly related to D₆-25(OH) D₃ clearance. We will test whether associations of CKD status with clearance are modified by race by including a CKD x race interaction term. If we find evidence of interaction, we will analyze each CKD x race category separately. Absent

interaction, we will test associations of each exposure in parallel (adjusted for each other) to maximize precision and power.

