SUBJECT SELECTION CRITERIA	
Inclusion Criteria:
 
 Age ≥ 18 years Self-reported race Caucasian, African American, or African Serum total 25(OH)D 10-50 ng/mL Chronic kidney disease status: Estimated GFR ≥60 mL/min/1.73m² (N=40) Estimated GFR <60 mL/min/1.73m², not treated with dialysis (N=40) End stage renal disease treated with hemodialysis (N=40) 
Exclusion Criteria:
 
 Primary hyperparathyroidism Gastric bypass Tuberculosis or sarcoidosis Current pregnancy Child-Pugh Class B or C cirrhosis (i.e. cirrhosis with ascites, hepatic encephalopathy, bilirubin ≥2 mg/dL, serum albumin ≤3.5 g/dL, or PT ≥ 4 seconds) History of kidney transplantation (unless failed transplant now treated with hemodialysis) Use of vitamin D₃, or vitamin D₂ supplements exceeding a mean daily dose of 400 IU, within 3 months (wash-out allowed) Use of 1,25(OH)₂D₃ or an analogue, calcimimetics, or medications known to induce CYP24A1 within 4 weeks (wash-out allowed) Serum calcium > 10.1 mg/dL Hemoglobin < 9 g/dL
TEST PRODUCT, DOSE, AND ROUTE OF ADMINISTRATION	
We will administer D₆-25-hydroxyvitamin D₃ Solution for Injection, 20 µg/mL intravenously. The deuterated 25(OH)D₃ is formulated using cosolvents to enhance solubility. Each mL contains 20 µg D₆-25(OH) D₃, 60% propylene glycol, 10% ethanol (ETOH) and water (30%) for injection, to volume. To ensure reliable detection of circulating deuterated 25(OH)D₃, without administering a dose that might alter the underlying

	
vitamin D metabolism, we aim to administer a dose that results in a peak deuterated 25(OH)D₃ concentration of approximately 5 ng/mL. The administered dose will be calculated as the targeted peak serum deuterated 25(OH)D₃ (5 ng/mL) multiplied by blood volume.

CONTROL PRODUCT, DOSE AND ROUTE OF ADMINISTRATION	There is no control product.
DURATION OF SUBJECT PARTICIPATION AND DURATION OF STUDY	
Subjects will be on study for approximately 12 weeks
 
Screening: approximately 4 weeks
 
Treatment: 1 day (subjects to the University of Washington Clinical Research Center)
 
Follow-up: 8 weeks
 
The total duration of the study is expected to be up to 3 years for subject recruitment and an additional 12 weeks for final subject follow-up.

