CONCOMMITANT MEDICATIONS	
Allowed:
 
 Vitamin D supplements (cholecalciferol, ergocalciferol) not to exceed a mean daily dose of 400 IU, within 3 months (wash-out allowed) 
Prohibited (within last 4 weeks, wash-out allowed):
 
 1,25(OH)₂D₃ or an analogue (e.g. paricalcitol, hectorol) Calcimimetics (e.g. cinaclacet) Medications known to potentially induce or inhibit CYP24A1 or CYP3A4
EFFICACY EVALUATIONS	None
PRIMARY ENDPOINT	
 Metabolic clearance of labeled 25(OH)D₃ (administered dose/AUC)
SECONDARY ENDPOINTS	
 AUC of labeled 25(OH)D₃ Terminal half-life of labeled 25(OH)D₃ Volume of distribution in the central compartment of labeled 25(OH)D₃
OTHER EVALUATIONS	Metabolic formation clearance (metabolite/parent AUC ratio) for metabolites of labeled 25(OH)D ₃
SAFETY EVALUATIONS	
Change in the serum concentrations of calcium, creatinine, AST, and ALT and from baseline to 7 days after 25(OH)D₃ administration
 
Incidence of adverse events

PLANNED INTERIM ANALYSES	This is not a clinical trial with an efficacy outcome, and it is neither randomized nor blinded. Formal interim analyses are not planned.
STATISTICS Primary Analysis Plan	We will examine the distribution of D ₆ -25(OH)D ₃ clearance by CKD status (3 categories) and race (2 categories) using box plots and summary statistics. We will test associations of CKD status and race with D ₆ -25(OH)D ₃ clearance (continuous outcome variable) using linear regression. Models will be adjusted for age, gender, diabetes status, body size, baseline 25(OH)D concentration, and other covariates strongly related to 25(OH)D ₃ clearance. We will test whether associations of CKD status with clearance are modified by race by including a CKD x race interaction term.
Rationale for Number of Subjects	Our power calculations conservatively assume an interaction between CKD status and race, for which each cell in the 3x2 recruitment grid would require individual comparison. With this approach, we estimate that 17 people in each of two groups will provide 80% power to detect a difference in D ₆ -25(OH)D ₃ half-life of 2 days, assuming a standard deviation of 2 days. We will recruit 20 people per cell to allow for multivariable adjustment.

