2 STUDY RATIONALE

Patients with chronic kidney disease (CKD) are at high risk of adverse health outcomes, including progression to end stage renal disease, cardiovascular disease events, and death.⁸ Impaired vitamin D metabolism is commonly observed in CKD and may contribute to the morbidity of this disease.¹ In healthy individuals, the kidney produces the majority of circulating 1,25-dihydroxyvitamin D₃ (1,25(OH)₂D₃, or calcitriol). Calcitriol binds the vitamin D receptors in diverse target tissues, and is known to modulate inflammation and fibrosis, suppress the renin-angiotensin system, and regulate proliferation and differentiation. In CKD, renal production of 1,25(OH)₂D₃ is reduced, resulting in secondary hyperparathyroidism and dysregulation of other organs and tissues. Our preliminary data suggest that clearance of vitamin D metabolites is also reduced in CKD.

Concentrations of vitamin D metabolites in blood and tissues must necessarily represent a balance of production and catabolism. While basic mechanisms of vitamin D catabolism have been defined,⁹ the clinical evaluation of vitamin D catabolism has received remarkably little attention. In health, CYP24A1 is the major enzyme responsible for catabolism of both 25(OH)D₃ and 1,25(OH)₂D₃.^{1,9-15} CYP24A1 is found in most tissues in the body and is rapidly induced by 1,25(OH)₂D₃ to prevent 1,25(OH)₂D₃ intoxication.¹⁶⁻¹⁸ As a result, CYP24A1 expression is commonly used as a marker of tissue 1,25(OH)₂D₃ activity in basic science.¹⁹⁻³⁵ However, the ability of vitamin D catabolism to reflect 1,25(OH)₂D₃ function has not been similarly harnessed for clinical use. Evaluation of circulating 24,25(OH)₂D₃ concentration may offer this opportunity. 24,25(OH)₂D₃ is the most abundant product of 25(OH)D₃ catabolism by CYP24A1.⁹ When viewed in the context of prevailing 25(OH)D₃, 24,25(OH)₂D₃ reflects CYP24A1 activity. 24,25(OH)₂D₃ circulates at high concentrations (generally 1-10 ng/mL)^{36,37} and has a circulating half-life of approximately 7 days.³⁸ Circulating 24,25(OH)₂D₃ appears to

come from both renal and non-renal sources.^{15,22,39-41} In the kidney proximal tubule, CYP24A1 transcription is induced by FGF-23 and suppressed by PTH.^{17,42}

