Vitamin D metabolism also differs substantially by race.⁵² The circulating concentration of 25(OH)D is substantially lower in people who define their race as African American or African compared to Caucasian populations, presumably due to differences in skin pigmentation and cutaneous cholecalciferol synthesis. Interestingly, the circulating concentrations of 1,25(OH)₂D₃ do not vary by race, although there are noted differences in bone density between the two populations. Data from our cohort suggest associations between low 25(OH)D levels and coronary heart disease among Caucasians, but not in African American or African populations. This data suggests that previously unrecognized differences in vitamin D catabolism may contribute to racial differences in disease susceptibility.

The goal of this study is to better understand vitamin D catabolism and how it is affected by CKD and race. Specifically, we will evaluate the metabolic clearance of 25-hydroxyvitamin D₃ in individuals with varying degrees of CKD and among participants who self-report their race as Caucasian, African American, or African. The long-term goal of this work is to enhance the clinical evaluation and treatment of impaired vitamin D metabolism.

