5 CRITERIA FOR EVALUATION

5.1 Primary Efficacy Endpoint

The primary outcome of interest is the metabolic clearance of labeled 25(OH)D₃.

We will measure serum concentrations of 24,25(OH)₂D₃, 25(OH)D₃, 25(OH)D₂, 1,25(OH)₂D₃ and 1,25(OH)₂D₂ at the University of Washington by mass spectrometry. For each participant and time point, a single serum aliquot is used to measure this panel of vitamin D metabolites using immunoaffinity extraction and HPLC-mass spectrometry (Xevo TQ, Waters Corp., Milford, MA) with deuterated internal standards.⁵³⁻⁵⁶

For each subject, non-compartmental analysis of plasma concentration versus time data will be performed using Phoenix software (Pharsight, Cary, NC). Clearance will be calculated as administered 25(OH)D₃ dose divided by 25(OH)D₃ AUC. We focus on clearance as our primary outcome because it reflects the metabolism of 25(OH)D₃ accounting for circulating 25(OH)D₃ concentration (units of volume/time, akin to creatinine clearance). Clearance is independent of volume of distribution, in contrast to $t_{1/2}$, which will be evaluated as a secondary outcome. Clearance will be evaluated with and without adjustment for body size.

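### Race is tested against 25(OH)D3 clearance only in models adjusted for baseline 25(OH)D, which is partly a result of clearance and differs by race; a paired model without it should be pre-specified

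*Combined protocol and SAP*

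**What the plan says.** Section 14.3 tests CKD status and race against clearance by linear regression, adjusting for age, gender, diabetes, "vitamin D supplement use (within eligibility criteria), body size, baseline 25(OH)D concentration, and other covariates strongly related to" clearance. The synopsis (Primary Analysis Plan) gives nearly the same list, without supplement use: "Models will be adjusted for age, gender, diabetes status, body size, baseline 25(OH)D concentration, and other covariates strongly related to" clearance.

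Section 14.3 then tests a CKD x race term. If there is interaction, each CKD x race category is analysed separately; if not, race and CKD are tested adjusted for each other. The covariates of the separate-category step are not restated, but no step drops baseline 25(OH)D. Section 14.4 carries the approach to the secondary endpoints.

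The unadjusted displays are box plots and summaries by race and CKD, and LOWESS, spline and box plots against covariates that include baseline 25(OH)D. The only with/without comparison promised is in section 5.1: "Clearance will be evaluated with and without adjustment for body size".

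On the covariate itself, section 2 says: "Concentrations of vitamin D metabolites in blood and tissues must necessarily represent a balance of production and catabolism". On race it says: "The circulating concentration of 25(OH)D is substantially lower in people who define their race as African American or African compared to Caucasian populations". The explanation it offers for this gap is one of supply: "presumably due to differences in skin pigmentation and cutaneous cholecalciferol synthesis". It also reports that serum 25(OH)D3 did not vary by eGFR in a pre-dialysis cohort of 278.

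**The concern.** Baseline 25(OH)D lies partly downstream of the outcome, and race is linked to it through production. Take two people with the same 25(OH)D, one of whom produces less: that person must also clear less. A regression comparing race groups at equal 25(OH)D makes this comparison on average, so it can show lower clearance in the group with lower production even when clearance is the same.

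The primary objective asks how catabolism is affected by CKD and race. With only the adjusted test, a race difference in vitamin D supply could be reported as a race difference in clearance. The plan does not say whether its race coefficient is the overall difference in clearance or the difference at a given 25(OH)D level. The two can disagree.

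**Working it through.** **The plan's own figure.** Section 14.6 gives 17 per group for a 2-day half-life difference with SD 2 days and 80% power. A two-sample t-test at two-sided 0.05 (alpha is not stated) gives 16.7, rounded up to 17, with power 80.7%. The figure reproduces, but it is an unadjusted half-life comparison and does not bear on this point.

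**Inputs from the documents.** 20 per cell, so 60 per race group; entry range 10-50 ng/mL (section 6.2); the covariates of section 14.3. The documents do not give these three quantities, so ranges are assumed:
- R: race ratio of 25(OH)D, 0.8 to 0.6.
- s: share of within-race variance of log 25(OH)D due to clearance, 0.05 to 0.30.
- e: elasticity of clearance on 25(OH)D, 0 to 0.25 (0 means that the level does not affect clearance).

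**Algebra at steady state.** Let D be 25(OH)D, P production, CL clearance, and u the part of log clearance not driven by D. Race acts on P only.
- lnD = lnP - lnCL and lnCL = e*lnD + u, so lnD = (lnP - u)/(1+e) and lnCL = (e*lnP + u)/(1+e).
- Total race effect on lnCL: e*lnR.
- Within-race slope of lnCL on lnD: e(1-s) - s.
- Race coefficient at equal lnD: e*lnR - [e(1-s) - s]*lnR = s(1+e)*lnR.

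| e | R | s | Race ratio with 25(OH)D | Race ratio without it |
|---|---|---|---|---|
| 0 | 0.8 | 0.05 | 0.8^0.05 = 0.989 (-1.1%) | 1 (0%) |
| 0 | 0.7 | 0.10 | 0.7^0.10 = 0.965 (-3.5%) | 1 (0%) |
| 0 | 0.7 | 0.30 | 0.7^0.30 = 0.899 (-10.1%) | 1 (0%) |
| 0.25 | 0.8 | 0.05 | 0.8^0.0625 = 0.986 (-1.4%) | 0.8^0.25 = 0.946 (-5.4%) |
| 0.25 | 0.7 | 0.10 | 0.7^0.125 = 0.956 (-4.4%) | 0.7^0.25 = 0.915 (-8.5%) |
| 0.25 | 0.7 | 0.30 | 0.7^0.375 = 0.875 (-12.5%) | 0.7^0.25 = 0.915 (-8.5%) |

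**Simulation with covariates.** 120 participants, 1,000 trials per setting, main-effects regression of clearance on race, CKD, age, gender, diabetes, supplement use and body size, with and without 25(OH)D. Assumed: geometric mean 28 ng/mL, residual log-SD 0.40, PK error 15%, assay error 10%, entry range applied, 25(OH)D not varying by CKD.
- e=0, R from 0.8 to 0.6: race significant with 25(OH)D in 5-8% (s=0.05), 8-20% (s=0.10) and 24-71% (s=0.30) of trials; without it in 5-14%.
- e=0, with mean 22 or 32 ng/mL or log-SD 0.30 or 0.50: 6-7% with and 5-6% without at R=0.8, s=0.05; 40-52% with and 7-13% without at R=0.7, s=0.30.
- e=0.25, R=0.7: 20% with and 47% without at s=0.10; 62% with and 50% without at s=0.30.

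**Simpler simulation** (60 per race group, log clearance, no other covariates, same entry range and errors), e=0:
- R=0.8, s=0.05: 6% with, 5% without.
- R=0.7, s=0.10: 15% with, 6-7% without.
- R=0.7, s=0.30: 59% with (-9.5%), 9% without (-3.0%). With the entry range removed, the last pair is 55% and 6%, so most of what remains without 25(OH)D comes from eligibility.

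**The case against.** The best case for the plan is that 25(OH)D may itself alter clearance. The synopsis keeps the tracer dose small, "without administering a dose that might alter the underlying" vitamin D metabolism. If so, the contrast at equal 25(OH)D is a legitimate question, and the model without 25(OH)D takes in differences that run through supply. By the formulas above, the adjusted ratio is closer to 1 than the other whenever s < e/(1+e), that is s < 0.20 at e=0.25. This stands, and it rules out a caution aimed at the adjusted model alone. It does not remove the concern: apart from the entry range, the model without 25(OH)D recovers the actual race difference in clearance whatever e is, and where e>0 that difference is real.

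Second, large distortion needs a sizeable s. Section 2 is compatible with a small one: 24,25(OH)2D3 fell from 3.6 to 1.7 ng/mL across eGFR while 25(OH)D3 did not vary. This also stands.

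Third, the planned plots would show readers the unadjusted race pattern and the relation of clearance to 25(OH)D. They would, but without a test and without adjustment for age, diabetes or body size.

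A reader might also infer from section 5.1, which picks clearance "because it reflects the metabolism of 25(OH)D₃ accounting for circulating 25(OH)D₃ concentration", that the covariate is redundant. The text does not support that. It explains clearance as a volume per time and does not say whether clearance varies with the 25(OH)D level.

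**Conclusion.** The point holds as a cheap improvement, with medium confidence. The only tested race contrast conditions on a variable that the protocol describes as partly a result of catabolism and lower by race. With clearance equal by race and e=0, the adjusted coefficient ranges from negligible (about -1%, rejection near 5-6%, at R=0.8, s=0.05) to material (about -10% at R=0.7, s=0.30, with rejection of 40-52% in the sensitivity runs with covariates and 59% in the simpler one). R, s, e, the spread of 25(OH)D and the error sizes are all assumptions.

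Three stronger readings are not supported. A reader might infer that the planned analysis will produce a false race finding; at small s it would not. A reader might infer that leaving out 25(OH)D gives an unbiased answer. At e=0 the entry range alone left -0.3% to -3.9% in that model, and at e>0 it includes supply effects. A reader might infer that the CKD contrast is equally affected. Section 2 suggests little exposure before dialysis; dialysis is not covered there. The argument extends to AUC and half-life, which depend on clearance, but is not shown for central volume of distribution.

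**What to change.** In section 14.3 and the synopsis, keep the planned sequence: test CKD x race first and, if there is no interaction, drop the term and test race and CKD adjusted for each other. Dropping it matters: with the term in, the race coefficient is a contrast within one CKD stratum (standard error 0.062 against 0.036 in a check, a ratio of 1.7, close to the square root of 3).

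At each step, pre-specify two models that share every covariate, including any others chosen for their relation to clearance, except that one omits baseline 25(OH)D.
- Without it: labelled as the total race (and CKD) association, including any difference running through vitamin D supply.
- With it: labelled as the contrast at equal 25(OH)D.

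Report both. Do not attribute a race difference to catabolism independent of vitamin D supply from either model alone. State that the 10-50 ng/mL entry range leaves some selection bias. Apply the same pair to AUC and half-life.

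The cost is a wording change, one extra model at each step and two race coefficients to explain; no new data are needed. The effect on precision is small: in the main-effects simulation the standard error of the race coefficient without 25(OH)D was 0.88 to 1.04 times that with it.

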9.1.6 Other Clinical Procedures

Physical activity will be ascertained by questionnaire and accelerometry between Study days 1 and 7. Vitamin D intake will be estimated by food frequency questionnaire at Baseline. Serum and plasma will be collected at Baseline to measure calcium and phosphorus, intact parathyroid hormone, fibroblast growth factor-23, and vitamin D binding protein. Two 24-hour urine collections will be obtained, immediately preceding and following administration of D₆-25(OH) D₃, to quantify urinary excretion of albumin and the metabolites of deuterated D₆-25(OH) D₃, respectively. Dialysis patients will be exempt from all urine collections. Adiposity will be measured by Dual energy X-ray absorptiometry at the baseline visit.

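### The CKD and race models admit any covariate strongly related to clearance, so PTH or FGF-23, which regulate the catabolic enzyme, could enter and change the CKD effect being estimated.

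*Combined protocol and SAP*

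**What the plan says.** Section 14.3 (Analysis of Primary Endpoint) tests CKD status and race against clearance by linear regression. The named adjusters are age, gender, diabetes, vitamin D supplement use, body size and baseline 25(OH)D. The list then stays open: "baseline 25(OH)D concentration, and other covariates strongly related to" clearance. The synopsis (Primary Analysis Plan) has the same open ending but leaves out supplement use. Neither place gives a threshold, a candidate list or a selection procedure.

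Earlier in the same paragraph of 14.3, clearance is explored against "age, gender, diabetes status, and baseline concentrations of 25(OH)D, PTH, FGF-23, and vitamin D binding protein". The next sentence reads "We will pay particular attention to the associations of PTH and FGF-23 with" clearance, "including multivariable modeling to determine independent associations". It does not say whether that modelling is separate from the CKD and race models.

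Section 2 (Study Rationale) says that in CKD renal production of 1,25(OH)₂D₃ "is reduced, resulting in secondary hyperparathyroidism and dysregulation of other organs and tissues". It calls CYP24A1 the major catabolic enzyme for 25(OH)D₃ and states that in the proximal tubule "CYP24A1 transcription is induced by FGF-23 and suppressed by PTH". Section 3.1 asks how catabolism is affected by CKD and race, without separating a total from a direct effect. Section 14.4 carries the same analysis to the secondary endpoints.

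**The concern.** Seven covariates are explored in 14.3. Four of them (age, gender, diabetes, 25(OH)D) are already named adjusters. The remaining three are PTH, FGF-23 and vitamin D binding protein, so they are the visible candidates for the open clause.

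For PTH, section 2 supplies every step: CKD raises PTH, PTH suppresses CYP24A1, and CYP24A1 clears 25(OH)D₃. A model that holds PTH fixed no longer estimates the overall difference between CKD groups. It estimates the part that does not run through PTH. For FGF-23, the documents give the step to CYP24A1 but not the step from CKD, so the effect of adjusting for it cannot be signed from the text.

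An analyst could follow 14.3 faithfully and report either quantity, and the choice would rest on what the outcome data showed. The adjusted regression is the only test planned for the primary question.

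**Working it through.** **The plan's own figure.** Section 14.6 gives 17 per group for 80% power, with a difference of 2 days and an SD of 2 days on half-life. The standardised effect is 2/2 = 1.0. A two-sample t-test at two-sided 0.05 (assumed; alpha is not stated) needs 16.7, so 17, and has 80.7% power at 17. The figure reproduces. It refers to half-life; I borrow only the ratio of 1 SD and apply it to clearance.

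**Inputs for the illustration.** From the documents: 20 per cell over two races, so 40 per CKD row. Assumed, because the documents give nothing: total hemodialysis versus eGFR ≥60 effect of -1 SD; a marker 2 SD higher in hemodialysis and midway in the middle row; within-row marker SD of 1; residual SD of 1; 30%, 50% or 70% of the effect running through the marker in the same direction.

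**Estimate.** Adjusted coefficient = total × (1 − share):
- 30%: -1.0 × 0.7 = -0.7
- 50%: -1.0 × 0.5 = -0.5
- 70%: -1.0 × 0.3 = -0.3

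**Standard error.** Without the marker: √(2/40) = 0.224. With it: √(2/40 + gap²/within-row sum of squares) = √(0.05 + 4/117) = 0.290, where 117 = 3 × 39. This is about 30% wider, even if the marker has no link to clearance within any row.

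**Detection at two-sided 0.05.** Without the marker, 1.0/0.224 = 4.47, about 99%. With it:
- 30%: 0.7/0.290 = 2.41, about 67%
- 50%: 0.5/0.290 = 1.72, about 40%
- 70%: 0.3/0.290 = 1.03, about 18%

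Simulation agrees within its error: coefficients of about -0.71, -0.50 and -0.31, and detection of 68%, 39% and 19%.

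**A marker acting in the opposite direction.** Suppose the marker's path adds +0.5 SD to clearance while the total stays at -1.0. The adjusted coefficient is -1.0 − 0.5 = -1.5. This would be the case for FGF-23 if CKD raised it, because FGF-23 induces CYP24A1.

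**How often such a marker would enter.** The clause has no threshold, so I tried three readings (same-direction marker, N = 120):

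| Reading of the clause | 30% mediated | 50% | 70% |
|---|---|---|---|
| Correlation of at least 0.5 in absolute value | 2% | 10% | 32% |
| p<0.05, conditional on CKD row | 36% | 76% | 96% |
| p<0.05, pooled over rows | 98% | about 100% | 100% |

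A pooled p<0.05 at N = 120 needs a correlation of only about 0.18.

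**The case against.** The plan does not place PTH or FGF-23 in the CKD model. Neither is a named adjuster, and their modelling has its own sentence and purpose, which fits the secondary objective on biochemical correlates (section 3.2). That can be read as the separation one would want. This stands: entry is permitted, not stated. A reader might infer that the plan will adjust the CKD effect away; the text does not support that.

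The size also follows from the inputs. The adjusted coefficient is simply one minus an assumed share, and section 2 confines the regulation by PTH and FGF-23 to the proximal tubule, while describing CYP24A1 in most tissues and hepatic routes through CYP3A4 and SULT2A1. Nothing in the documents puts 30% to 70% of the effect through PTH, or makes PTH and FGF-23 the main regulators of clearance overall. This stands too, so the figures are illustrative. A high entry rate holds only under a lenient screen.

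Box plots and summary statistics by CKD status are planned, so unadjusted differences would be visible. That softens the consequence but does not settle which quantity is tested.

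Two further readings go too far. One is that a urine covariate would remove the hemodialysis row, since "Dialysis patients will be exempt from all urine collections"; but 14.3 names no urine variable. The other is that vitamin D binding protein must be barred as a consequence of CKD; no section says that it is one.

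**Conclusion.** The concern holds as a gap in the adjustment rule, not as a stated error. Section 14.3 lets the outcome data decide which covariates join the primary test, and PTH, which the protocol itself places between CKD and catabolism, is among the variables explored. Adjusting for PTH would shrink the CKD effect that the primary objective asks about. For FGF-23 the safe word is distorted: the documents do not say that CKD raises it, and its documented action on CYP24A1 is opposite to that of PTH.

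The direction for PTH follows from the protocol's own account. The amount of shrinkage and loss of detection rests on the assumed share, gap and effect, and the chance of entry runs from 2% to 100% with the share and the reading of the clause. This should be fixed because the correction is cheap and removes an ambiguity from the only planned test. In an observational pharmacokinetic study with unadjusted summaries also planned, it does not invalidate the design, and it calls for no change in sample size.

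**What to change.** Delete the open clause from 14.3 and the synopsis. In both places give the same closed list of covariates already named: age, gender, diabetes status, body size, baseline 25(OH)D and vitamin D supplement use. This also removes the present mismatch over supplement use. The list should be described as fixed in advance, not as preceding CKD, because participants are enrolled with existing disease.

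State that PTH and FGF-23 are not in the primary models that test CKD and race. Report models that add them separately, labelled as explanatory; this keeps the plan's stated interest in their independent associations.

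The cost is wording: no new data or visits. The downside is that a covariate that explains residual variance may be left out of the primary model; it can be shown in a sensitivity model.
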